3.2. Sample Size Determination

The following assumptions were used in the Protocol Version 6 sample size calculations:

- Exponential survival curves, placebo survival estimate of 0.6 at 8 years with a hazard ratio of 0.60, and total study duration of 10 years (from first subject enrolled), allowing for 4 years of subject accrual and 6 years of follow up.
- Subjects will be randomized in a 1:1 ratio to placebo or OCA.
- The 2 treatment groups will be compared using a 2-sided log rank test at the 5% level of significance.
- Two interim analyses and one final analysis are planned, with interim analyses occurring after the accrual of 50% and 75% of clinical outcome events, respectively.
- A dropout rate of 10% is assumed

Based on the randomization ratio, significance level, and assumed hazard ratio, a total of 127 events (both groups combined) was to provide 80% power to demonstrate a statistically significant difference between OCA and placebo on time to liver-related outcomes, including all-cause mortality.

In addition, based on the remaining assumptions stated above, it was estimated that approximately 428 subjects would be enrolled to attain 127 events.

Sample size calculations were based on the following composite endpoint: time to first occurrence of death, liver transplant, MELD ≥ 15 , uncontrolled ascites, or hospitalization for new onset or recurrence of variceal bleed, hepatic encephalopathy, or spontaneous bacterial peritonitis.

Due to enrollment challenges and difficulties to keep patients in the study, the trial will be terminated early by sponsor. To better evaluate the benefit-risk ratio, the composite endpoint will be revised to include additional components that occur earlier in the progression of PBC

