8.1. Primary Efficacy Endpoint

The following table identifies the elements of the intercurrent events and strategies to address for primary efficacy endpoint.

Primary Estimand	
Population	Adult subjects with PBC who are at higher risk of liver-related clinical complications.
Endpoint (variable)	
Compare the effect of OCA to placebo, in conjunction with established local standard of care, on the composite clinical outcomes as measured by time from randomization to the first occurrence of the following post-randomization events:
 
Group 1 (applies to all subjects):
 
 • Death (all-cause) • Liver transplant • Hospitalization (as defined by a stay of 24 hours or greater) for new onset or recurrence of: 
 – Variceal bleed – Hepatic encephalopathy (as defined by a West Haven score of ≥ 2) – Spontaneous bacterial peritonitis (confirmed by diagnostic paracentesis OR presence of $>250/\text{mm}^3$ PMNs in the ascitic fluid) – Bacterial empyema (confirmed by diagnostic thoracentesis OR presence of $>250/\text{mm}^3$ PMNs in the pleural fluid) • Uncontrolled or refractory ascites (requiring large volume paracentesis) • Portal hypertension syndromes (hepatorenal, portopulmonary, and hepatopulmonary) • MELD-Na score ≥ 15 (for subjects with baseline MELD-Na score < 12) • MELD score ≥ 15 (for subjects with baseline MELD-Na score ≥ 12) 
Group 2 (applies to subjects without decompensation at baseline):
 
 • Progression to decompensated liver disease (for subjects without decompensation at baseline). See Section 2.1.1 Group 2 and Section 8.1.1 for prioritization list and analysis. 
Group 3 (applies to subjects without decompensation or clinical evidence of portal hypertension at baseline):
 
 • Progression to clinical evidence of portal hypertension without decompensation (for subjects without decompensation or clinical evidence of portal hypertension at baseline). See Section 2.1.1 Group 3 and Section 8.1.1 for prioritization list and analysis.

Primary Estimand		
Intercurrent events/ Strategies to address	Use of commercial OCA as concomitant medication or IP/study visit discontinuation due to commercial OCA use	Treatment policy will use for primary analysis: Treatment effect regardless of intercurrent event.

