8.1.2. Sensitivity Analyses

The following sensitivity analyses will be carried out on the primary endpoint, with different population, strategy to handle the intercurrent events, or summary.

No.	Population	Strategies to address intercurrent events	Population-level summary
1	Subset of primary population, who had no major protocol violations.	Same as primary analysis	Same as primary analysis
2	Same as primary analysis	Same as primary analysis	The 2 treatment groups will be compared using the win ratio (Pocock 2012) using the unmatched method within the bilirubin randomization strata. The 95% confidence interval will be calculated using a bootstrapping method and a p-value will be calculated using the stratified Finkelstein-Schoenfeld test (Finkelstein 1999).
3	Same as primary analysis	Data collected after the intercurrent events to be excluded (while on treatment policy)	For subjects who didn't experience an event before the intercurrent event, multiple imputation will be carried out for time to event based on the available data after the intercurrent event. Details is included in the appendix.
4	Same as primary analysis	Exclude data after 90 days after a patient discontinues IP.	Same as primary analysis.
5	Same as primary analysis	Include only data prior to when a patient starts commercial OCALIVA.	Same as primary analysis.
6	Same as primary analysis	Include only data prior to when OCA was commercially available in the subject's country.	Same as primary analysis.
7	Same as primary analysis	Hypothetical strategy, ie, as if the intercurrent events didn't happen.	Hazard ratio and 95% CI will be estimated using a weighted Cox regression model with Sandwich estimator. The derivation of the weights based on Inverse Probability of Censoring Weighting (IPCW) is detailed in the appendix.

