Moderate - Total Bilirubin > ULN and Albumin ≥ LLN or

Total Bilirubin \leq ULN and Albumin $<$ LLN

Severe – Total Bilirubin $>$ ULN and Albumin $<$ LLN, where baseline values of total bilirubin and albumin are taken to be the average of all pre-dose measurements.

- The CLIF-C ADs is derived using the following formula:

$$\text{CLIF-C ADs} = 10 \times 0.03 \times [\text{Age (years)}] + 0.66 \times \ln[\text{creatinine (mg/dL)}] + 1.71 \times \ln[\text{INR}] + 0.88 \times \ln[\text{WBC (} 10^9 \text{ cells/L)}] - 0.05 \times [\text{sodium (mmol/L)}] + 8.$$

Inverse Probability of Censoring Weighting

The hazard ratio will be estimated using Inverse Probability of Censoring Weighting (IPCW) techniques (Robins 1999). Baseline predictors of both censoring and clinical outcome will be identified in advance. Augmented IPCW estimators described by Robins may be implemented to explore the possible impact of unmeasured confounding. Baseline predictors of both censoring and clinical outcome for the IPCW analysis are:

- Treatment Group: OCA/Placebo
- Age (year) at Screening Visit
- Sex: Male/Female
- UDCA use at Screening Visit: Yes/No
- Liver biochemistry at Baseline (alkaline phosphatase (ALP) (U/L), alanine transaminase (ALT) (U/L), aspartate transaminase (AST) (U/L), total bilirubin ($\mu\text{mol/L}$), albumin (g/L), and platelets)

The post-baseline time-varying covariates are ALP, ALT, AST, total bilirubin, and AE of pruritus with severity of moderate and severe.

To derive the IPCW weights, the patient's follow-up time up until the time of censoring or event occurring will be partitioned into about 10 intervals. The probability of remaining uncensored at the end of each time interval adjusted for baseline variables, and post-baseline time-varying covariates will be estimated using a pooled logistic regression model. To avoid possible extreme values when taking the inverse of the estimated probabilities from the pooled logistic model with both baseline and time-varying post-baseline covariates, the inverse of these probabilities will be stabilized by multiplying the probability of remaining uncensored conditional only on baseline covariates. Once the IPCW weights are derived, the hazard ratio of treatment effect and corresponding 95% CI will be estimated using a weighted Cox regression model with Sandwich estimator to obtain the robust estimate of the variance-covariance matrix of the parameter estimates.

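### Sensitivity analysis 7: one pooled IPCW weight model for both arms, with few time-varying markers, can leave switching bias in the hazard ratio if the reasons for censoring differ by arm

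*SAP*

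**What the plan says.** SAP Section 8.1 names two intercurrent events. The first is "Use of commercial OCA as concomitant medication or IP/study visit discontinuation due to commercial OCA use"; the second is stopping investigational product for other reasons while remaining in follow-up. The primary analysis handles both by treatment policy. Row 7 of the table in Section 8.1.2 takes a different line, "Hypothetical strategy, ie, as if the intercurrent events" had not occurred, and estimates the hazard ratio by a weighted Cox model. Section 8.2 repeats the sensitivity analyses, apart from the win ratio, for the endpoint that is primary for the EMA filing, so row 7 is run there too.

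The weights are specified in Appendix A (Inverse Probability of Censoring Weighting). The probability of remaining uncensored over about ten intervals "will be estimated using a pooled logistic regression model". The baseline predictors are treatment group, age, sex, UDCA use, ALP, ALT, AST, total bilirubin, albumin and platelets. On post-baseline information the text is: "The post-baseline time-varying covariates are ALP, ALT, AST, total bilirubin, and AE of pruritus with severity of moderate and severe". It mentions no interaction with treatment, no fit by arm and no truncation of the weights. An augmented estimator is optional.

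**The concern.** Treatment group can be a predictor only if both arms are in the same regression. With no interaction stated, a given bilirubin or ALP value is taken to change the chance of censoring equally in the two arms. The sponsor's documents make that doubtful. Section 3 of the interim SAP uses as its example placebo subjects who stop and start marketed OCA. Section 6.2 treats informative censoring linked to commercial OCA as a concern, and Section 6.3 has the DMC look at censoring by arm and disease severity. Moderate or severe pruritus in the covariate list suggests that tolerability is a second driver.

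The time-varying list also leaves out markers that feed the endpoint. In the SAP's MELD formula the coefficients are 11.2 for ln INR, 9.57 for ln creatinine and 3.78 for ln bilirubin, yet INR and creatinine are not in the weight model at all. Albumin and platelets enter at baseline only. Sections 8.3.2, 9.4.1 and 9.4.2 show that all four are measured at study visits.

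What is at stake is how row 7 is read. If it agrees with simple censoring because the weight model is wrong, the agreement looks like robustness.

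**Working it through.** **The plan's own figures.** The SAP gives no figure for the IPCW analysis. Its design figures (Section 3.2) were checked because they supply the effect size used below.
- Inputs: "The 2 treatment groups will be compared using a 2-sided log rank test at the 5% level of significance"; "placebo survival estimate of 0.6 at 8 years with a hazard ratio of 0.60"; "Subjects will be randomized in a 1:1 ratio to placebo or OCA"; "a total of 127 events (both groups combined) was to provide 80% power"; 10% dropout; 4 years of accrual plus 6 of follow-up.
- Freedman: D = (1.96 + 0.842)² × [(1 + 0.60)/(1 − 0.60)]² = 7.85 × 16 ≈ 126, against 127 stated.
- Subjects: the placebo hazard is −ln(0.6)/8 = 0.0638 per year and the OCA hazard 0.6 × 0.0638 = 0.0383. With P = 1 − (e^(−6λ) − e^(−10λ))/(4λ), the event probabilities are 0.399 and 0.263, mean 0.331. Then 127/0.331/0.9 ≈ 427, against 428 stated.

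Both reproduce.

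**Simulation of the weight model.** The SAP gives no switching rates or drivers, so every strength here is assumed. There were 15,000 subjects per arm, four replicates, ten intervals, a direct hazard ratio of 0.60 and stabilised weights. The outcome model was adjusted for baseline covariates. An intercurrent event occurred in 32–49% of placebo and 38–46% of OCA subjects. The marker stands for a time-varying liver marker that is not in the SAP's list.

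| Assumed drivers of censoring | True | Plain censoring | As listed | By arm, same covariates | By arm, marker added |
|---|---|---|---|---|---|
| Differ by arm, marker moderate on placebo | 0.630 | 0.703 | 0.713 | 0.638 | 0.620 |
| Differ by arm, marker strong on placebo | 0.611 | 0.720 | 0.729 | 0.647 | 0.608 |
| Differ by arm, all measured | 0.626 | 0.647 | 0.653 | 0.597 | 0.596 |
| Placebo driven only by the marker | 0.604 | 0.640 | 0.641 | 0.642 | 0.610 |
| Same in both arms, plus marker | 0.624 | 0.587 | 0.601 | 0.602 | 0.618 |
| Same in both arms, all measured | 0.627 | 0.611 | 0.615 | 0.614 | 0.614 |
| Placebo unrelated to prognosis | 0.617 | 0.617 | 0.616 | 0.618 | 0.618 |

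The share of bias left is ln(estimate/true) ÷ ln(plain censoring/true).
- Row 1: ln(0.713/0.630) = 0.124 against ln(0.703/0.630) = 0.110, so 113% remains. By arm, 0.013/0.110 leaves about 11%.
- Row 2: 0.177/0.164 leaves 108%; by arm, 0.057/0.164 leaves 35%.
- Row 5: 0.038/0.061 leaves about 62%; the full model leaves 18%.
- Adding the marker to the single model without splitting by arm gave 0.716 and 0.736 in rows 1 and 2, which is no gain.

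The third row needs care, because with four replicates the by-arm fit appears to overshoot. Repeating the same code with 24 replicates gave true 0.620, plain censoring 0.659, listed 0.666 and by arm 0.609, so most of that overshoot was simulation noise. The fourth row shows the converse: if placebo switching follows only an unlisted marker, splitting by arm does nothing until the marker is added.

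**A second simulation, with stronger assumptions.** It had 8,000 subjects and six runs. About 54% of placebo was censored in relation to a marker, and about 25% of OCA unrelated to it. True 0.64, plain censoring 0.88, single model 0.83, by arm 0.66. Under no effect: 1.01, 1.39, 1.29 and 1.02.

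**One dependency.** Appendix A does not say that the weighted Cox model adjusts for the baseline covariates in the stabilising numerator. Without that adjustment the listed model gave 0.91 and 0.99 in the first two rows, against true unadjusted values of 0.67 and 0.64.

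**The case against.** Several stronger readings are tempting, and the documents do not support them.

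- **That switching bias stays largely in the hazard ratio.** This depends on drivers the SAP does not report. In the table the residual bias runs from all of it to none that matters.
- **That row 7 is the only analysis aimed at informative switching.** Row 6 cuts the data when OCA became available in the subject's country, a date not set by that subject's own prognosis. Row 3 imputes event times after the intercurrent event. Rows 4 and 5 add further cuts.
- **That treatment is fixed as a main effect only.** Appendix A lists it as a predictor and is silent on interactions. A main effect is the natural reading, but interactions are not excluded.
- **That separate models by type of intercurrent event are needed.** With drivers differing by arm and two censoring types, splitting by event type gave 0.659 against 0.658 for splitting by arm alone (true 0.640).

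The covariate list was not careless. ALP, bilirubin and pruritus are plausible drivers, bilirubin enters MELD, and the same list came into the interim SAP in an amendment answering agency comments (Section 9). Precision also limits the practical weight. At about 334 subjects (Clinical Pharmacology Analysis Plan, Section 5), one run had a log hazard ratio standard deviation of about 0.24. A common-model bias of ln(0.72/0.64) ≈ 0.12 is about half of that.

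These points limit the size and reach of the concern. They do not answer it: the written model has no means of handling drivers that differ by arm, and the optional augmented estimator is not a commitment.

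**Conclusion.** The point holds in a limited form. As written, the weight model can leave material switching bias in the hazard ratio of sensitivity analysis 7 if the drivers of censoring differ by arm. Under the assumed arm-differing drivers with an omitted marker, the listed model did no better than plain censoring (0.71 and 0.73 against 0.63 and 0.61). Arm-specific fits with the same covariates removed roughly 65–90% of the bias. When drivers are common and measured, or placebo switching is unrelated to prognosis, the listed model does no material harm. All sizes rest on assumed rates and strengths.

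Only row 7 is affected, for the SAP primary endpoint and for the EMA primary endpoint. The primary log-rank test and hazard ratio follow treatment policy and do not change, and Section 8.6 allots no alpha to row 7. This is a worthwhile, inexpensive improvement to a supporting analysis.

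**What to change.** In Appendix A:

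1. Fit the numerator and denominator weight models separately in each arm, or include treatment-by-covariate interactions for the time-varying terms.
2. Secondarily, add time-varying albumin, platelets, INR and creatinine (or MELD), which are already collected.
3. Report the distribution of the weights by arm and pre-specify a truncation rule, for example at the 1st and 99th percentiles.

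The cost is SAP wording and some programming, with no new data. The weights may become somewhat more variable and the interval wider, although the by-arm fit did not increase the standard deviation in the run at about the enrolled sample size.

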14. DEVIATIONS FROM PROTOCOL

14.1. Primary Efficacy Endpoint and Analysis

Due in part to high discontinuation rates and requests from sites to close, the decision was made to stop 747-302 early, at approximately 67% information (84 adjudicated Protocol Version 6 endpoints observed). To increase the number of endpoint events and power to detect a difference, the primary efficacy endpoint has been expanded to include:

- Portal hypertension syndromes (hepatorenal, portopulmonary, or hepatopulmonary)
- Progression to decompensated liver disease (for subjects without decompensation at baseline)
- Progression to clinical evidence of portal hypertension without decompensation (for subjects without decompensation or clinical evidence of portal hypertension at baseline).

The primary efficacy analysis remains the stratified log rank test. With the inclusion of additional endpoints that occur earlier in the course of the disease, the log rank test is limited to each subject's first event, which is likely to be an outcome of lesser clinical importance. A win ratio analysis was added as a sensitivity analysis, to allow for a hierarchical comparison of the composite endpoints. The win ratio analysis allows for the comparison of more severe events such as death and liver transplant to be prioritized over the comparison of earlier-stage events such as progression to clinical evidence of portal hypertension.

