Multiple Imputation (Missing Not At Random) Description

The event rate during off-treatment period (after the treatment discontinuation and before the study close-out) is calculated. The survival time during off-treatment period is assumed to follow exponential distribution of calculated event rate. The survival time during off-treatment

period is added to the survival time during on-treatment period for those subjects who require imputation (ie, early terminators). If the total duration is longer than the period from randomization to study close-out, the survival time will be imputed to the study close-out as a censored observation. Otherwise, the survival time will be imputed to the date of event. Multiple imputation is used to impute the survival time by 5000 iterations.

Procedures:

Step	Description
1	From the ADSL dataset restricted to ITT population (ITTFL='Y'), extract patient identifiers (USUBJID), randomization date (RANDDT), randomized treatment (TRT01PN), death date (DTHDT), treatment (TRT01PN) start (TRTSDT) and stop (TRTEDT) date for treatment, study termination date (WTHDRDT), date of last contact (LASTDT), follow-up after treatment discontinued (FUFL), and stratification factors. Sort dataset by USUBJID.
2	From the efficacy analysis dataset (ADTTE), select the primary endpoint event. Select patient identifiers (USUBJID), randomized treatment (TRT01PN), the censoring indicator (CNSR), follow-up length (ADY), and last contact date (ADT). Sort dataset by USUBJID.
3	Identify patients that discontinued study drug (IPDISC='YES') from the ADDS dataset. Retain USUBJID, analysis start date (ASTDT), and IPDISC variables. Sort dataset by USUBJID.

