4	
Merge ADSL, ADTTE, and ADDS data together to create a dataset for analysis named EFF1.
 
 • Create a variable for start of close out period (e.g., 12 Feb 2022). • Assess if last contact date (ADT) is non-missing and less than end of study date 
 ○ If ADT non-missing and less than study end and patient was censored in the primary analysis then create a variable called COMPLETER and assign a value of 0 (study termination). ○ If ADT non-missing and greater than study end date, or the ADT is greater than the closeout date, or if non-censored in primary analysis then create a variable called COMPLETER and assign a value of 1 (primary endpoint event/completed study). • Assess if patient discontinued study medication (IPDISC='YES'), or was randomized and not treated, and evaluate this based on the censoring status in primary analysis and the COMPLETER status described above. • If IPDISC='YES' and patient was censored in primary analysis (CNSR=1) and did not complete the study (COMPLETER=0) then create a variable indicating the follow-up data will be imputed for the patient (IMPUTE=1). 
 - Create a variable called EVENT and set to missing to hold the censoring indicator used in analysis following multiple imputation. - Create a variable called T2EVENT and set to missing to hold the follow-up time used in analysis following multiple imputation. - Create a variable called T0 to hold the follow-up time from primary analysis (T0=ADY)

Step	Description
	
- Create a variable called T1 to hold the follow-up time from primary analysis (if DTHDT>. then T1=DTHDT – ADT + 1, otherwise T1= 12 Aug 2022 – ADT + 1).
 
 • If patient had a primary endpoint event in the primary analysis (CNSR=0), or completed the trial (CNSR=1 and COMPLETER=1), or patient did not discontinue drug prior to start of close out period (IPDISC ^= ‘YES’) and COMPLETER=1) then create a variable indicating the follow-up data will be not imputed for the patient (IMPUTE=0). 
- Create a variable called EVENT and set equal to 1 (EVENT=1) if patient experienced a primary endpoint event in primary analysis (CNSR=0), and 0 otherwise (EVENT=0).
 
- Create a variable called T2EVENT and set to equal to the follow-up time from primary analysis (T2EVENT=AVAL).
 
Sort dataset by treatment (TRT01PN) and randomization strata

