5	
For patients with IPDISC='Y', and remained in follow-up after discontinuation (ADT>TRTEDT and (DTHDT=. or DTHDT> ADT)), or for patients randomized and not treated that remained in follow-up IPDISC='Y' and (ADT>. and TRTSDT=. and (DTHDT=. or DTHDT> ADT)), sum the number of primary endpoint events (EVENT) by treatment group and randomization strata. Output dataset named EFF_COUNT.

6	
For those same patients from Step 5 sum the person-years of follow-up from discontinuation (TRTEDT) or from RANDDT (when TRTSDT=.) to the earliest of a primary endpoint event, last visit, death, or start of close out period (ADT). Output dataset named EFF_EXP.

7	
Create a dataset called EFF_RATE merging EFF with EFF_COUNT and EFF_EXP by treatment group and primary analysis strata. Derive hazard rates for primary endpoint event for each patient in a new variable named RATE. Set RATE=365.25*(primary endpoint event sum/follow-up time sum).

8	
Create a new dataset called IMPUTE from EFF_RATE restricted to patients that required follow-up imputation (IMPUTE=1). Derive 5,000 follow-up times for each patient for imputation in a variable named T2 as T2 is the randomly sampled from the exponential distribution given the event rate. When generating the exponential random variate specify a SEED equal to 1234 prior to derivation of T2. Assign the sequence of the T2 generated to a variable named ITERATION.

9	
Create a dataset called IMPUTE2 from the IMPUTE dataset. For each of the 5,000 observations created in Step 8, derive variables EVENT=1 and T2EVENT=T0+T2 if T2 is less than the time from study termination (LASTDT) to the earlier of the start of close out period or (post-termination) death (T2< DTHDT - LASTDT if DTHDT>, or T2<Aug 12, 2022 – LASTDT). Otherwise, set T2=0 and T2EVENT equal to the time from randomization to the earlier of the start of close out period, or post-termination) death (whichever occurs first). Here T2EVENT= DTHDT - RANDDT+1 if DTHDT> LASTDT, otherwise T2EVENT=Aug 12, 2022 – RANDDT+1

10	
Create 5,000 (virtual) datasets called IMPUTE3 by concatenating IMPUTE2 (for each iteration) with EFF with restriction to subjects that did not terminate the study (separately). For each of the 5,000 datasets perform a primary analysis (fit a stratified Cox model or KM method). Save parameter estimates for each iteration, and save the iteration variable.

Step	Description

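### The imputation titled missing not at random is missing at random given arm, stratum and IP status, so loss tied to unobserved prognosis goes untested

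*SAP*

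**What the plan says.** In SAP Section 8.1.2, analysis 3 states that "multiple imputation will be carried out for time to event based on the available data after the intercurrent event", and refers to the appendix for details. Appendix A gives them under the title "Multiple Imputation (Missing Not At Random) Description".

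- **Who is imputed (Step 4).** Subjects who stopped IP, were censored in the primary analysis and left before the end of the study: "did not complete the study (COMPLETER=0) then create a variable indicating the follow-up data will be imputed for the patient (IMPUTE=1").
- **Donors (Step 5).** Subjects who stopped IP "and remained in follow-up after discontinuation".
- **Rate (Steps 5-7).** The numerator is an instruction to "sum the number of primary endpoint events (EVENT) by treatment group and randomization strata". The denominator is an instruction to "sum the person-years of follow-up from discontinuation (TRTEDT") up to the earliest of event, last visit, death or close-out. RATE is the ratio of the two, times 365.25.
- **Draw (Step 8).** "The survival time during off-treatment period is assumed to follow exponential distribution of calculated event rate". Each imputed subject gets 5,000 exponential times at RATE, unmodified.

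Neither the appendix nor Section 8.1.2 gives a multiplier, a shift, a reference-arm rate or a tipping-point search.

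**The concern.** A missing-not-at-random analysis lets unobserved outcomes differ from observed ones after conditioning on everything that was observed. Here the conditioning variables (arm, stratum, IP stopped) are all observed, and within them leavers and followed discontinuers are given one hazard. That is a missing-at-random assumption, so the property named in the title is absent.

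Loss matters in this trial. Section 14.1 says the study was stopped early "Due in part to high discontinuation rates and requests from sites to close". Section 3.2 cites difficulty keeping patients in the study. Interim SAP Section 6.2 names informative censoring as a concern for the primary analysis. Suppose OCA subjects who leave contact are sicker, in ways not captured by arm, stratum and IP status, than OCA discontinuers who stay in contact. The primary analysis and analysis 3 would then both err in favour of OCA, and a reader trusting the title could take the second as a check on the first.

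**Working it through.** **1. What the steps assume.** For arm a and stratum s, RATE(a,s) = donor events / donor off-IP person-time, and T2 ~ Exponential(RATE(a,s)). Let k be the true hazard of leavers after loss, divided by that of followed discontinuers in the same arm and stratum. Nothing observed after loss enters RATE, so the imputed hazard ratio cannot respond to k. It is right only at k = 1.

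**2. Whether another row of Section 8.1.2 varies k.**
- Row 1 changes the population.
- Row 2 (win ratio) treats pairs left undecided by censoring as non-informative.
- Rows 4-6 truncate the data.
- Row 7 weights on the measured covariates listed in Appendix A. Augmented IPCW is mentioned there only as something that may be done, without specification.

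None varies k.

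**3. Inputs from the plan.** The plan gives no figure for this imputation. Section 3.2 supplies the event rate for a simulation, and its own sizing was checked first.
- Placebo hazard: -ln(0.6)/8 = 0.0639 per year. OCA on treatment: 0.60 x 0.0639 = 0.0383.
- Events (Freedman): (1.960 + 0.842)^2 x (1.6/0.4)^2 = 126, against 127 stated.
- Subjects: event probability per arm = 1 - [exp(-6h) - exp(-10h)]/(4h), averaging 0.331. 127/0.331 = 384, and 384/0.90 = 427, against 428 stated.

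**4. Simulation of Steps 5-10 as intended** (units aligned, no death filter, no strata; 240,000 subjects per cell, point estimates only). These inputs are assumptions and are not in the SAP: IP stopped at 0.15 per year; administrative follow-up of 2-7 years; off-IP hazard 0.0639 in both arms; 30%, 50% or 70% of stoppers leave at once, so that about 13%, 22% or 30% of all subjects leave; k applies to OCA leavers only.

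| Leaving | k | Full-data HR | Censoring at loss | Planned imputation | Imputation with OCA RATE x k |
|---|---|---|---|---|---|
| 13% | 1 | 0.703 | 0.680 | 0.703 | 0.703 |
| 13% | 2 | 0.779 | 0.680 | 0.706 | 0.778 |
| 13% | 3 | 0.846 | 0.691 | 0.715 | 0.846 |
| 22% | 1 | 0.718 | 0.669 | 0.719 | 0.719 |
| 22% | 2 | 0.836 | 0.669 | 0.713 | 0.834 |
| 22% | 3 | 0.926 | 0.663 | 0.712 | 0.933 |
| 30% | 1 | 0.700 | 0.633 | 0.699 | 0.699 |
| 30% | 2 | 0.877 | 0.649 | 0.725 | 0.898 |
| 30% | 3 | 1.024 | 0.641 | 0.710 | 1.018 |

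The planned imputation stays at 0.70-0.73 throughout. With the multiplier set to k, it follows the full-data value to within about 0.02.

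**5. A second simulation** (200,000 per arm, on-treatment HR 0.6, no off-treatment effect, 19% or 29-30% lost) gives full-data HRs of 0.785 and 0.824 at k = 2, and 0.842 and 0.946 at k = 3. The planned imputation gives 0.689-0.699.

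**6. The rate itself.** Step 9 compares T2 with a difference of dates and adds it to a follow-up time in days, so T2 needs a rate per day. Step 6 sums person-years and Step 7 multiplies by 365.25, which does not give one. Step 5 also requires the death date to be missing or later than ADT. If ADT is the event date, a donor whose first event is death is dropped and RATE is too low.

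**The case against.** A reader might infer that analysis 3 says nothing about informative loss. The documents do not support that. Leavers receive an off-IP rate, not the hazard of everyone still at risk, and this removes bias that runs through stopping IP. At k = 1 with 22% leaving, censoring gives 0.67, while imputation and full data both give 0.72. It is a legitimate retrieved-dropout analysis.

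The title also has a reading within the plan. Interim SAP Section 4.2 pairs censoring at last contact with a missing-at-random assumption, and imputing at a different rate departs from that reference. This explains the label but does not make it accurate, because IP status is observed.

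Donors and leavers are not cleanly separate. Step 5 asks only for some contact after the last dose, so a subject followed off IP for a while and then lost contributes donor time too. That softens the contrast, but the hazard after loss is still fixed at the donor rate.

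A reader might also take the simulated gap as the bias in this trial. It is not. An imputation without a departure parameter is flat in k by construction, and the size of the gap comes from assumed values. The SAP's only dropout figure is the 10% planning assumption. High discontinuation is not the same as loss of contact: Section 3 expects subjects off IP to be followed to closure, and Section 8.1.1 counts record review and semi-annual calls as contact. Nor does the SAP say that agreement between the analyses will be reported as robustness to every kind of loss.

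**Conclusion.** The point stands in a limited form. Analysis 3 handles loss that is informative through IP discontinuation. It is missing at random given arm, stratum and IP status, so its title is wrong, and the prespecified set contains no test of loss tied to unobserved prognosis beyond those factors. The actual bias is unknown. With about 20-30% lost and OCA leavers at 2-3 times the hazard of followed OCA discontinuers, the full-data HR is 0.79-0.95 under one set of assumptions and 0.84-1.02 under the other, against roughly 0.70 from the planned imputation. The flatness in k follows from the steps themselves; the sizes rest on the assumed loss, hazards and k. This should be corrected, but it does not touch the primary analysis or its significance level.

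**What to change.** 1. Rename the procedure as imputation at the observed off-treatment rate, missing at random given arm, stratum and IP discontinuation. Keep it.
2. Put Steps 6-9 on one time unit, and confirm that the Step 5 death condition does not remove donors whose first event is death. Until this is done, a multiplier on RATE cannot be interpreted.
3. In Step 8, draw T2 from RATE x delta over a prespecified grid, for example delta = 1 to 4, extended if no tipping point is reached. Run it in OCA alone (placebo at 1) and in both arms.
4. Report the delta at which significance at the Section 8.6 level (two-sided 0.041) is lost, beside the number lost per arm. One fixed RATE serves all 5,000 draws, so its own uncertainty is not carried into Rubin's rule. State this next to the tipping value.

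The cost is somewhat more programming than a single multiplier, because the rate has to be put right first. The reported robustness may also look less favourable. If the database is already locked, Section 1 requires the addition to be identified as post hoc.
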